9.8 Randomization

Participants eligible for inclusion in the study according to the screening will have the baseline measurements collected followed by a randomization carried out by the study investigator/study personnel.

A total of 231 participants will be randomly allocated in a 1:1:1 ratio to one of the following three groups:

- 1) BCC
- 2) ABC-ACC
- 3) Control

Randomization will be performed by the investigator at visit 1 (V1) after the baseline examination. Participants will be randomly assigned to one of three groups with a 1:1:1 allocation by use of a computer-

generated randomization schedule in REDCap. The randomization list will be generated and kept securely by the clinical responsible investigator. The randomization is done by stratifying the participants based on sex and HbA1c at baseline. The randomization is done in blocks in to order to ensure an equal number of participants in each group.

9.9 Patient outcome

Expected patient outcomes are improved glycaemic control. All participants will be offered their personal study test results after they have completed the study period.

9.10 Study feasibility

SDCC has the facilities to carry out the study. SDCC has a kitchen for patient education called “FoodLab” designed to carry out group education programs with hands-on activities to practice food and self-management skills related to diabetes e.g. courses in BCC and ABC-ACC.

The Capital Region of Denmark treats approx. 4,200 patients with T1D of which 3000 patients are treated at SDCC. Approximately 500-1000 patients with T1D have already attended an education program in either BCC or ABC-ACC. At least eight courses in BCC and eight courses in ABC-ACC are needed for education of 77 participants in each of the two group-based interventions based on the assumption that we can recruit 10 patients with T1D for each course not taking into account potential relatives and patients participating. During the last four years, 120 patients with T1D have attended the BCC program at SDCC on a yearly basis corresponding to 12 courses per year. Since the courses at SDCC are available for all 5,000 patients with T1D in the Capital Region of Denmark in 2018, we plan to implement 18 courses in either BCC or ABC-ACC per year equal to 180 patients per year.

One or two new courses will be initiated every third week at SDCC for patients with T1D except for holiday periods. Patients who do not wish to participate in the study or who do not fulfil the inclusion criteria will be included in the courses together with study participants. Additionally, some relatives will also be offered the opportunity to attend the courses, if patients need extra support to manage dietary changes based on an individual assessment by the principle study investigator.

10 Examinations

All patients found eligible for inclusion in the study will be invited to a first study visit (V1) for collection of baseline measurements up to four weeks before the intervention according to study specific SOPs. Subsequently, all participants will be randomized to one of the three study groups. All examinations will be performed in the outpatient diabetes clinic at SDCC. Study visits and examinations are described in detail in **table 1** below and in the current section.

Table 1: Schematic overview of study visits

Visit no Time, week no from start of intervention	Contact	Screening	V1 -4 to -1	V2 0	V3 2	V4 12	V5 24	V6 48	Described in section
Participant-related information									
Study information	X								9.6
Informed written consent		X							9.7
Eligible for inclusion and exclusion		X							9.7
Randomization		X							9.8
Efficacy outcomes									
HbA1c		X	X			X	X	X	10.2
Plasma lipids			X				X	X	10.2
Body weight			X			X	X	X	10.1
Height			X						10.1
Waist and hip circumference			X				X	X	10.1
Blood pressure			X				X	X	10.1
Blood samples, fasting			X				X	X	10.2
Blood samples, non-fasting	X				X				10.2
Urine samples for 4 days			X				X		10.3
CGM including PG for 6 days			X				X		10.4
DXA			X				X		10.5
Questionnaires & Forms									
F: Dietary registration for 4 days			X				X		10.6
Q: Diet-related quality of life			X				X	X	10.7
Q: Perceived Competencies in Diabetes			X				X	X	10.7
Q: Health-Care Climate			X				X		10.7
Q: Carbohydrate estimation accuracy			X				X	X	10.7
Q: Mathematical literacy			X				X	X	10.7
Q: Demographic data			X						10.9
Q: Physical activity			X				X	X	10.10
Intervention									
BCC				X	X	X			9.3.1
ABC-ACC				X	X	X			9.3.2
Standard individual dietary counselling				X	X	X			9.3.3

Abbreviations CGM=continuous glucose monitoring d=day; DXA=Dual-energy-X-ray absorptiometry; F=forms; no=number; PG=plasma glucose; Q=Questionnaire; V=visit.

10.1 Clinical Examination

Body weight will be measured at visit V1 (baseline), V5 (week 24) and V6 (week 48) in a fasting condition and at V4 (week 12) in a non-fasting condition. Height will only be measured and recorded at V1. Blood pressure, waist and hip circumference will be performed at visits V1, V5 and V6 in a fasting condition. Procedures will be conducted after appropriated training of study personnel involved in carrying out the procedures.

Body weight will be measured with the participant wearing light indoor clothes and no shoes at the same calibrated scale after emptying the bladder. Two measurements are made and both are noted to the nearest 0.1 kg. The average of the two measurements is used in further analysis.

Height is measured using a wall-mounted stadiometer with the participants not wearing shoes and with the heels, buttocks and upper part of the back remaining in contact with the wall/back of the stadiometer. Two measurements are made and both results are noted to the nearest 0.1 cm. The average of the two measurements is used in further analysis.

Waist circumference is measured halfway between the lowest point of the costal margin and highest point of the iliac crest at the end of expiration with the participant in a standing position. All anthropometric measurements are performed twice with the average of the two measurements used in further analysis.

Hip circumference is measured at the level of the greater femoral trochanter; both are measured to the nearest 0.5 cm at the end of expiration with the participant in a standing position. All anthropometric measurements are performed twice with the average of the two measurements used in further analysis.

Blood pressure is measured with the participant in sitting position after minimum 10 min of rest, not talking during the measurement. Blood pressure measurements are repeated three times separated by two min breaks. Mean values are calculated.

10.2 Blood Samples

Participants must attend V1, V5 and V6 after 8-10 hours of fasting having consumed only water for collection of blood samples. A small venous catheter will be inserted in one of the participant's arms for blood sampling which will be performed by a trained biomedical laboratory technician in the Clinical Biochemical Department at SDCC. The samples will be used for assessment of C-peptide, triglycerides, total cholesterol, HDL-C, LDL-C, very-low-density-lipoprotein cholesterol (VLDL-C), HbA1c, haemoglobin, creatinine, albumin, potassium, sodium, alanine aminotransferase (ALAT), thyroid-stimulating hormone (TSH), cobalamin and alkaline phosphatase according to standard procedure. No tobacco smoking is allowed in the morning before the visit. HbA1c will also be measured at V4.

10.3 Urine Samples

At V1 and V5 the participants will be provided with oral and written instructions on how to collect urine samples as midstream urine spots four times daily (preferably in the morning, afternoon and evening) for four days (three of which are the same days as the participants record their dietary food intake, while wearing a CGM). Participants are asked to hand in the urine collection in person at the laboratory at SDCC no later than one week after the urine has been collected. Urine samples are analysed for content of albumin and creatinine as well as excretion of biomarkers related to carbohydrate intake (sucrose, fructose, mannose and lactose) and qualitative markers of common groups of carbohydrate rich foods including vegetables, fruit, whole grain, and possibly potato, beet root, and rice.

10.4 Continuous Glucose Monitoring

The iPro®2 CGM system will be used. The CGM will be inserted under the skin on the lower part of the abdomen (under the umbilicus) by the investigator or study personnel at V1 and V5 for use in a period of six days. Participants will receive a glucometer together with oral and written instructions about how to measure glucose levels four times a day while wearing the CGM. Measurements are to be taken before breakfast, before lunch, before main evening meal and before bedtime. Participants are asked to hand in the CGM together with the urine collection or at V2 after baseline measurements and by mail or in person after six days of use after V5.

10.5 Body fat distribution

A DXA scan will be performed at V1 and V5 to measure body composition. A pregnancy test will be performed in all fertile women at V1 according to national requirements and procedures for X-ray equipment. At V5 a urine pregnancy test will be performed if a menstrual period is missed or if pregnancy is suspected. If the test is positive, the scan will not be conducted and the participation in the study is stopped immediately. The DXA scan will be performed in a fasting state with the participants only wearing light clothing and after emptying the bladder. The participant will lie still on a table while a machine arm passes over their entire body, which emits a high- and a low-energy X-ray beam. By measuring the absorption of each beam into parts of the body, readings for bone mineral density, lean body mass and fat mass will be obtained. The same device and software will be used for all participants throughout the study and must be calibrated according to manufacturer's instructions. The DXA scan will be conducted by the investigator or study personnel that have completed the mandatory course for non-medical staff operating DXA.

10.6 Dietary assessment

Participants are asked to complete four days of weighed dietary food records after V1 and V5. Participants will receive oral and written instructions about how to record their food intake in the same four days as they collect their urine and while wearing a CGM, preferably on four consecutive days including three weekdays and one day in the weekend to capture a representative weekly diet for assessment of total energy and macronutrient intake. All food and beverages consumed during the three days of recording must be noted in a dietary registration form with as many details as possible. In addition, pre- and post-meal plasma glucose levels, insulin type and dose as well as physical activities are noted (appendix 6). The exact amount of the food should be determined preferably by weighing the food on a digital scale, but in situations where this is not possible (e.g. when dining out) the estimated portion size using household measurements or other well-defined units will be accepted. Participants are asked to hand in the dietary registration form in person together with the urine collection or at V2 for baseline measurements and by mail or in person after V5.

Instructions for the dietary registration will be giving by study personal with a nutritional background well trained in performing and assessing dietary food records. After receiving the dietary registration forms the records will be visually inspected immediately for clarification of possible misunderstandings. Subsequently, the nutrient intake based on the dietary records will be calculated using the software system *Vitakost* (Vitakost Aps, Kolding) where nutrient and energy calculations are based on the Danish national food database. The dietary food records are used to estimate total energy intake (kJ/d), intake of carbohydrates, protein and fat (g/day and g/meal), added sugar (g/d) and total dietary fibre intake (g/d).

10.7 Questionnaires

Questionnaires on diabetes diet-related quality of life questionnaire (DDRQOL) (appendix 7), Perceived Competencies in Diabetes Scale (PCS) (appendix 8), Health-Care Climate Questionnaire (HCCQ) (appendix 9), accuracy in carbohydrate portion size estimation assessed by a carbohydrate photographic questionnaire (CPQ) (appendix 10), mathematical literacy based on a mathematical literacy test (appendix

11), and level of physical activity as assessed by International Physical Activity Questionnaire Short Form (IPAQ SF) (appendix 12) will be send out electronically through the software system REDCap before visits V1, V5 and V6. Participants preferring to fill in the questionnaires at the study site will be offered access to a tablet or laptop at SDCC and support by study personnel as needed.

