9.3 Interventions

9.3.1 Basic carbohydrate counting intervention

Intervention (The BCC program)

Composition of the program:

- Two 180 min interactive group sessions
- One 120 min interactive follow-up session

The BCC program consists of two sessions of three hours two weeks apart and a follow-up session of two hours after 10 weeks delivered by trained dietitians. In addition to the BCC program, the participants are receiving regular care in the diabetes clinic at SDCC or their usual diabetes clinic in the Capital Region of Denmark for a total of 48 weeks.

The BCC program is a group-based educational program based on several years of experience at SDCC. The BCC program uses trained dietitians following a planned curriculum which include experience-based learning with problem-solving exercises, hands-on activities, short theoretical presentations, discussions of motivational aspects and coping strategies. The BCC program integrates peer modelling, skill development, goal setting, observational learning and social support into the program content and activities. The training includes identifying carbohydrates in food, reading carbohydrate tables, calculating the carbohydrate content from food labels, tables and apps for smartphones and use of a personalized carbohydrate plan with guiding suggestions for daily intake of carbohydrates at meals based on 3-days of personal dietary recording

performed before the program including plasma glucose measurements and prandial insulin dosages taken. An app from the Danish Diabetes Association (*Diabetes og Kulhydrattælling*®). The Danish Diabetes Association's app for estimating of carbohydrates, Pragma soft A/S, available in Google Play® and AppStore® 12/2014, Free) will be introduced to support estimation and calculation of carbohydrates and assist in simple insulin dose determination if participants choose to consume more carbohydrates at a meal than suggested in their personal carbohydrate plan.

The participants in the sessions will be a mixture of study participants and patients not enrolled in the study. The courses in carbohydrate counting, funded by the Novo Nordisk Foundation, targets all patients with T1D treated in the capital region of Denmark, and runs in the period 2018-2020. Close relatives are included in the sessions if participants or patients need extra support to manage dietary changes based on an individual assessment by the principle study investigator.

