10.9 Other baseline demographics

The following self-administered questions on baseline demographics will be sent out electronically before V1 using the software system REDCap (appendix 13).

[figure not shown]
- Educational level
- Main occupation
- Civil status and household composition
- Yearly income

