11.3 V1: Baseline (week -4 to -1)

At visit 1 the following procedures and assessments will be performed in the morning after 8-10 hours fast:

- Collection of fasting blood samples
- Measurement of height, body weight, blood pressure, hip and waist circumference (fasting condition)
- Pregnancy test (woman only)
- Full body DXA scan (fasting condition)
- A meal is provided for the participant
- Fill in questionnaire concerning demographic data, CPQ, Mathematical literacy test, DDRQOL, PCS, HCCQ, IPAQ SF at V1
- Collection of medical history including registration of glucose- and lipid-lowering medicine
- Instruction in how to fill out the three days of dietary registration forms
- Instruction in how to collect four days of urine sample and how to hand in the sample
- Injection of CGM device and instruction in precautions and how to hand in the CGM
- Instruction in recording four daily PG measurements in six days with CGM

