11.7 V5: After 24 weeks of intervention

At visit 5 the following procedures will be performed in the morning after 8-10 hours fasting:

- Collection of fasting blood samples
- Measurement of body weight, blood pressure, hip and waist circumference (fasting condition)
- Check for pregnancy (women only)
- Full body DXA scan (fasting condition)
- A meal is provided for the participant
- Participants who has not filled in all questionnaires before V5 will be asked to fill in at V5
- Update of glucose- and lipid-lowering medicine
- Instruction in how to fill out the three days of dietary registration forms
- Instruction in how to collect four days of urine sample and how to hand in the sample
- Injection of CGM device and instruction in precautions and how to hand in the CGM
- Instruction in recording four daily PG measurements in six days with CGM

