11.8 V6: Follow-up at 48 weeks (24 weeks after completing the intervention period)

At visit 6 the following procedures will be performed in the morning after 8-10 hours fasting:

- Collection of fasting blood samples
- Measurement of body weight, blood pressure, hip and waist circumference (fasting condition)
- Update of glucose- and lipid-lowering medicine
- Participants who has not filled in all questionnaires before V6 will be asked to fill in at V6
- A meal is provided for the participant

12 Laboratory Analyses

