#### **Secondary/descriptive/exploratory outcomes**

The treatment effect will be given as the baseline corrected difference between the groups at V2 and V3. No minimal clinically relevant differences were defined for these outcomes.

- HbA1c, mmol/mol (only for V3)
- Blinded CGM data (not measured at V3)
  - Mean amplitude of glycaemic excursions (MAGE), mmol/l
  - Mean plasma glucose, mmol/l
  - Time in range (TIR): % of readings and time 3.9-10.0 mmol/l
  - Time above range (TAR): % of readings and time 10.1-13.9 mmol/l (level 1 – high)
  - Time above range (TAR): % of reading and time >13.9 mmol/l (level 2 – very high)
  - Time above range: % of readings and time >13.9 mmol/l
  - Time below range (TBR): % readings and time 3.0-3.8 mmol/l (level 1 – low)
  - Time below range (TBR): % readings and time <3.0 mmol/l (level 2 – very low)
  - Glycaemic variability, coefficient of variation (CV), %
- BMI (kg/m^2)
- Body weight (kg)
- Waist/Hip ratio, unitless
- Blood pressure
  - Systolic blood pressure (mmHg)
  - Diastolic blood pressure (mmHg)
- LDL cholesterol (mmol/l)
- Median carbohydrate estimation errors, g
- Median carbohydrate estimation errors, %
- Self-reported diabetes diet-related quality of life (DDRQOL), total score within each subscale
  - General perception of diet

- Satisfaction with diet
- Restriction of social functions
- Burden of dietary therapy
- Perceived benefits of dietary therapy
- Mental health
- Vitality
- Self-reported Perceived Health Competence in Diabetes Scale (PCDS), total score
- Self-reported Healthcare Climate Questionnaire (HCCQ) (not measured at V3), total score

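### The carbohydrate photo test may be taken unobserved before V5 and V6, with no stated rule on aids, after the BCC arm has been taught tables and an app

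*Protocol*

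**What the plan says.** **Mode of administration.** Protocol section 10.7 groups the CPQ and the mathematical literacy test with the quality-of-life, competence, health-care climate and activity scales. All of them "will be send out electronically through the software system REDCap before visits V1, V5 and V6". There is an alternative: "Participants preferring to fill in the questionnaires at the study site will be offered access to a tablet or laptop at SDCC", with staff help where required.

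**Visit lists.** Section 11.3 includes this item among the V1 procedures: "Fill in questionnaire concerning demographic data, CPQ, Mathematical literacy test, DDRQOL, PCS, HCCQ, IPAQ SF at V1". Section 11.7 reads "Participants who has not filled in all questionnaires before V5 will be asked to fill in at V5", and section 11.8 reads "Participants who has not filled in all questionnaires before V6 will be asked to fill in at V6".

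**Teaching.** Section 9.3.1 has BCC participants learn to work out carbohydrate content from labels, tables and smartphone apps, and an app from the Danish Diabetes Association "will be introduced to support estimation and calculation of carbohydrates". Section 9.3.2 gives ABC-ACC participants a quick introduction to BCC and an automated bolus calculator. Section 9.3.3 allows control counselling to cover carbohydrate amounts, but names neither tables nor an app.

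**Outcome status.** Carbohydrate estimation accuracy is a secondary outcome in protocol section 9.1.2. SAP Section 6 lists "Median carbohydrate estimation errors, g" (and the same in per cent) among the secondary/descriptive/exploratory outcomes, analysed as a difference between groups corrected for baseline. Numeracy appears in the SAP only in a supplementary table. SAP visits V2 and V3 are the protocol's V5 (week 24) and V6 (week 48).

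**The concern.** The CPQ has right and wrong answers. An attitude scale can be filled in anywhere, but the result of a skill test depends on the conditions under which it is taken. If participants answer at home, unobserved, some can look up the foods shown. Such a score mixes unaided skill with access to aids.

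This matters most when access differs by arm, and here the BCC programme itself teaches the aids. Section 9.5.2 excludes people who already practise carbohydrate counting, so familiarity with such tools is likely to come largely from the allocated programme.

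Estimation accuracy is part of the mechanism that main hypothesis 1 proposes for BCC. If the secondary result favours BCC, a reader would want to know whether participants estimate better or looked the answers up. The plan as written could not tell them.

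**Working it through.** The documents state no figure on this point, so the check compares sections and then asks what bias the comparison could carry.

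1. **Where is the test taken at V5 and V6?** Sections 10.7, 11.7 and 11.8 agree. The test is sent out beforehand, and on-site completion is for those who prefer it or have not finished. Completion before the visit is the default.

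2. **Where is it taken at V1?** Section 10.7 sends it out before V1 as well, while section 11.3 lists it as done at V1. The section 11.3 bullet does not settle the matter, because it also lists demographic data, and section 10.9 says that "self-administered questions on baseline demographics will be sent out electronically before V1 using the software system REDCap". Being listed under V1 therefore does not show that an item was completed on site. The sections conflict.

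3. **What governs aids?** The available text gives no supervision, time limit or rule on aids for the CPQ. The SAP (Other outcomes) collects self-reported tool use for meals at V1, V2 and V3, but not tool use during the test. The SAP plans no additional analyses.

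4. **Which arms have been taught aids by V5?** For BCC, tables and an app, explicitly. For ABC-ACC, a short BCC training with a dosing calculator; carbohydrate tables and app are not named. For control, neither is named and neither is ruled out.

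5. **What bias follows?** Let *p* be the share of an arm that uses an aid during the test at V5, and *d* the mean reduction in error among those who do. With equal true skill, the apparent advantage of BCC over control is

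   (*p* in BCC − *p* in control) × *d*.

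   - A shift in setting between V1 and V5 that is common to all arms cancels from this difference. It would alter the within-group changes, which section 9.1.2 and the SAP also report.
   - Teaching starts at V2, so aid use at V1 should be balanced across arms in expectation. The between-arm bias therefore does not depend on how the V1 conflict is resolved.
   - The bias is zero if aid use is equal across arms or the aids do not help.

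6. **How large could it be?** Neither input is in the documents. As an illustration only, assume that aid use is 10 to 30 percentage points higher in BCC and that an aid lowers error by 20 percentage points. Then 0.10 × 20 = 2 and 0.30 × 20 = 6 points of apparent improvement without any gain in skill. These figures show how the inputs combine; they do not estimate what happened in this trial.

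**The case against.** The strongest reply is that unequal aid use is possible but not shown.

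- **The app is open to everyone.** Section 9.3.1 describes it as free in public app stores, and control counselling may cover carbohydrate amounts. This stands as a limit on size. It does not remove the asymmetry, because only BCC is explicitly taught the tools.
- **An aid may not help much.** The CPQ assesses portion-size estimation from photographs, and protocol section 6.1 says that technology cannot yet replace self-estimation for most meals. This also stands as a limit on size. A table or app may still help convert a judged portion into grams of carbohydrate.
- **The rules may exist elsewhere.** Appendices 10 and 11 were not available, and section 14.4 promises study-specific procedures and training to standardise measurement. The absence of a rule is therefore shown only for the text at hand. Likewise, staff help is mentioned alongside the tablet and laptop and may be purely technical; coaching by staff cannot be inferred.
- **Aided estimation may be the intended outcome,** since using tools is part of what BCC teaches. That would be legitimate, but the plan would have to say so and apply the same conditions to every arm.
- **The outcome is not primary.** This is correct. The superiority and equivalence claims concern HbA1c and MAGE, and no planned analysis carries the CPQ score into them.

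**Conclusion.** The concern holds for the CPQ and for comparisons involving BCC. By default the test is done before V5 and V6 without observation, no rule on aids or record of their use is given in the available text, and by then BCC has been taught tables and an app. Aided answers could pass as better estimation accuracy in a secondary outcome tied to main hypothesis 1. The direction favours BCC if its participants use aids more often and the aids help; both conditions are assumptions. The size is unknown. HbA1c and MAGE are unaffected.

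A reader might infer three stronger points that the documents do not support:

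- **That baseline skill is tested on site and follow-up skill at home.** Section 10.7 sends the tests out before V1 too, so this is an unresolved conflict with section 11.3 and not an established feature of the design.
- **That both trained arms, and only they, were taught the app and tables.** This is explicit for BCC, indirect for ABC-ACC and not excluded for control.
- **That the numeracy result is biased in the same way.** The mathematical literacy test shares the inconsistency in mode. However, nothing shows that a carbohydrate app or table helps with it, and an ordinary calculator is open to every arm.

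This is worth correcting because the remedy is cheap, not because bias has been demonstrated.

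**What to change.** **Protocol.** Reconcile section 10.7 with sections 11.3, 11.7 and 11.8. Take the CPQ out of the pre-visit mailing and, for consistency, the mathematical literacy test as well. Have all arms complete both on the study tablet at V1, V5 and V6 under the same conditions. For the CPQ, allow no apps or carbohydrate tables. Limit staff to technical help. The other questionnaires can still be sent ahead.

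**Data already collected.** From the REDCap timestamps, report by arm the share of tests completed before the visit day, and state the limitation next to the estimation-accuracy result. A timestamp shows when a test was completed, not where. Treat any analysis of on-site completers as supportive only: they are people who preferred the site or had not finished beforehand, a self-selected subset formed after randomisation.

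**Cost.** Participants already attend V1, V5 and V6, and tablets are already offered. The change needs short edits to four protocol sections and a line in the SAP. The price is slightly longer visits and some missing tests when a visit is not attended.
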